Binocular Over Refraction			x
Distance, Intermediate, and Near ETDRS LogMAR Visual Acuity			x
Collection of Unworn Lenses (if applicable)		x	x
Study Completion			x

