2.26.	Insertion of Study	Provide the subject with a new set of lenses	

Visit 2: Treatment 1 Follow-Up 1			
Step	Procedure	Details	
	Lenses	that match the power of the lenses that were discarded in step 2.24 above.	
2.27.	Post-Fit Questionnaire	The subject will evaluate the vision characteristics, comfort characteristics, handling characteristics, and visual symptoms of the study lenses using the PRO questionnaire.	
2.28.	Exit Distance and Near Visual Acuity	Distance and near Snellen visual acuity will be measured OD, OS, and OU to the nearest letter with the study contact lenses in place. For near measures use the ETDRS 2000 Series Chart 1 or 2. The acuity will be recorded to the nearest letter OD, OS and OU. Note: The distance visual acuity must be at least 20/30 OU for the lenses to be dispensed.	
2.29.	Dispensing Criteria	The lenses will be dispensed for 6-8 days. 
 Distance Snellen acuity equal to or better than 20/30 OU Subject must indicate that the vision is acceptable. Subject must indicate that the comfort of the lenses is acceptable. Lenses must have an acceptable toric and general lens fit. 	
2.30.	Subject Instructions	Instruct the Subject the following: 
 The lenses will be worn on a daily wear basis. Only enough lenses will be dispensed to the subject to wear for the required number of days until their follow-up visit. No additional lenses will be dispensed. A new lens will be opened and worn each day. Instruct the subject to bring back all unworn study lenses. No cleaning or disinfecting solutions will be used. If determined necessary by the Investigator sterile non-preserved rewetting drops may be dispensed to be used as needed 	

Visit 2: Treatment 1 Follow-Up 1			
Step	Procedure	Details	
		
for dryness.
 
 • Subjects will be instructed to wear lenses for a minimum of 6 hours a day, every day during the study. • Subjects will be instructed to wear their glasses when not wearing the study lenses. 
Note: In the event a lens is lost or damaged, the subject will return to the investigator site for replacement. As much as reasonably possible, a damaged lens should be returned to the investigational site and then returned to the Sponsor. If lens damage is present, complete the Product Quality Complaint Form. The lens will be stored in labeled vial with sterile saline, and returned to the Sponsor.
	

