2.31.	Schedule Follow-up	
The subject will be scheduled to return for their follow-up appointment in 7±1 day.
 
Note: To count the follow-up visit as a day of wear the Subject must have worn the study lenses for 6 hours prior to the visit.
	

VISIT 3

The subjects must present to Visit 3 wearing the study lenses. To be counted as a day of wear the lenses need to have been worn for at least six (6) hours prior to the visit.

Visit 3: Treatment 1 Follow-Up 2			
Step	Procedure	Details	
3.1.	Adverse Events and Concomitant Medications Review	Review any changes to the subject's medical history or concomitant medications from the previous study visit. Record any changes, and any adverse events.	
3.2.	Wear time and Comfortable Wear time (Study Lenses)	Record the average wearing time and comfortable wearing time with the study lenses.	
3.3.	Compliance	Confirm compliance with the prescribed wear schedule.	
3.4.	PRO and CLDEQ-8 Questionnaires	The subject will respond to the Follow-Up PRO and Dry Eye Questionnaires.	
3.5.	Subject Reported Ocular Symptoms	Subjects will respond to a verbal open-ended symptoms questionnaire.	
3.6.	Subjective Acceptance	Record whether the subjects distance and near vision with the lenses is acceptable.	
3.7.	Entrance Distance and Near Visual Acuity	Record the distance Snellen visual acuity with the contact lenses (OD, OS, and OU) to the nearest letter. For near measures use the ETDRS 2000 Series Chart 1 or 2. The acuity will be recorded to the nearest letter OD, OS and OU.	
3.8.	Binocular Distance Over-refraction and Distance Visual Acuity	Perform a binocular over-refraction and record the OD and OS results and distance visual acuity. Note: No lens changes are allowed based on the over-refraction.	
3.9.	Toric Fit Evaluation	After lens settling, record: 
 • The rotational position to the nearest degree • Lens stability with blink • Lens stability with eye versions • Toric fit acceptable or unacceptable Toric lens fit will be unacceptable if lenses rotated more than 40 degrees, or lens stability is worse than 5 degrees movement with blink. If toric fit is unacceptable, remove, store, and label the lenses, and proceed to final evaluation. 	
3.10.	Subjective Lens Fit	Evaluate and grade lens centration, primary gaze	

Visit 3: Treatment 1 Follow-Up 2

Step	Procedure	Details	

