	Assessment	
movement, upgaze movement and tightness (push-up test).
 
 • The subject should not proceed to wear the lenses if any of the following is observed: • presence of limbal exposure (appearance of clear cornea) in any gaze • presence of edge lift • presence of unacceptable movement (excessive or insufficient) in all three movement categories (primary gaze, upgaze, and push-up). 
If either lens is deemed unacceptable, the subject will be discontinued from the study. Remove the lenses, perform a slit-lamp evaluation, and complete the Final Evaluation form.
	
3.11.	Visual Performance Distance (3M) Intermediate (64 cm) Near (40 cm)	
Visual performance will be recorded OD, OS, and OU for the following:
 
Distance, Bright Illuminance ETDRS Charts 3M-HC#1, HC#2, HC#3 and LC#1, LC#2 and LC#3
 
Near, Bright Illuminance Reduced Guillon-Poling Charts High Contrast and Low Contrast Intermediate (64 cm) and Near (40 cm).
 
Distance, Dim Illuminance (with Distance goggles) ETDRS Charts 3M-HC#4, HC#5, HC#6
 
Near, Dim Illuminance (with Near goggles) Reduced Guillon-Poling charts High Contrast Intermediate (64 cm) and Near (40 cm).
 
Note:
 
 • The room illuminance must be between 7.3 and 7.9 EV. • Distance, HC-1 Chart luminance Acceptable EV Range 10.5-10.7. • Guillon-Poling, Near Chart Luminance Acceptable EV Range 10.8-11.1. • Do not use the Mesopic filter for Dim 	

Visit 3: Treatment 1 Follow-Up 2			
Step	Procedure	Details	
		luminance (Dim luminance will be simulated by using the goggles).	
3.12.	Collection of unworn lenses (if applicable)	Collect unworn lenses returned by the subject.	
3.13.	Lens Removal	Have the subject remove the study lenses and store in saline in a labeled glass vial. Note: Lenses do not need to be stored in a refrigerator.	
3.14.	Slit Lamp Biomicroscopy	FDA Slit Lamp Classification Scale will be used to grade the findings and determine eligibility. For the conjunctival redness [REDACTED] 0.5-unit increments will be used in the grading. Corneal Staining Assessment [REDACTED] will be graded in 1.0 increments. If the clearance of the fluorescein needs to be expedited, preservative-free rewetting drops or saline may be instilled.	[REDACTED]

FINAL EVALUATION

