8.2. Withdrawal/Discontinuation from the Study

A subject will be withdrawn from the study for any of the following reasons:

- Subject death during the study period
- Subject withdrawal of consent
- Subject not compliant to protocol
- Subject lost to follow-up
- Subject no longer meets eligibility criteria (e.g. the subject becomes pregnant)
- Subject develops significant or serious adverse events causing discontinuation of study lens wear
- Subjects who have experienced a Corneal Infiltrative Event (CIE)

- Investigator's clinical judgment regarding the subject safety reasons (that it is in the best interest of the subject to stop treatment)
- Subject missed two consecutive study visits
- Subject not compliant with study lens wear schedule
- Subject not successfully dispensed due to lack of efficacy and safety including poor vision, poor comfort or unacceptable fit

For discontinued subjects, the Investigator will:

- Complete the current visit (scheduled or unscheduled)
- Complete the Final Evaluation, indicating the reason that the subject was discontinued from the study
- Record the spherocylindrical refraction with best corrected distance visual acuity
- Collect used test article(s) (worn or brought to the visit) from the subject and discard them, unless otherwise stated in Section 7.2
- Collect all unused test article(s) from the subject

An additional subject may be enrolled if a subject discontinues from the study prematurely.

In cases where a subject is lost to follow-up, every possible effort must be made to contact the subject and determine the reason for discontinuation/withdrawal. The measures taken to follow up must be documented including two written attempts and a certified letter (or equivalent) as the final attempt.

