14. STATISTICAL METHODS

14.1. General Considerations

All data summaries and statistical analyses will be performed using the SAS software Version 9.4 or higher (SAS Institute, Cary, NC). Throughout the analysis of data, the results for each subject/eye will be used when available for summarization and statistical analysis. Unscheduled visits will be summarized separately and will be excluded from the statistical analysis.

Summary tables (Descriptive statistics and/or frequency tables) will be provided for all baseline variables, efficacy variables and safety variables as appropriate. Continuous variables will be summarized with descriptive statistics (n, mean, standard deviation (SD), median, minimum and maximum). Frequency count and percentage of subjects or eyes within each category will be provided for categorical data.

Summaries will be presented by study lens type and will be performed separately by completion status. All analyses will be conducted on per-protocol population (see Section 14.3).

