14.3. Analysis Populations

Safety Population:

All subjects who were administered any test article excluding subjects who drop out prior to administering any test article. At least one observation should be recorded.

Per-Protocol Population:

All subjects who have successfully completed all visits and did not substantially deviate from the protocol as determined by the trial cohort review committee prior to database hard lock (Per-Protocol Population). Justification of excluding subjects with protocol deviations in the per-protocol population set will be documented in a memo to file.

Intent-to-Treat (ITT) Population:

All assigned subjects regardless of actual treatment and subsequent withdrawal from study or deviation from protocol. At least one observation should be recorded.

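### At Visit 3 a failed fit check takes the lenses off before the study's only logMAR measurement, and Section 8.2 gives a conflicting instruction

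*Combined protocol and SAP*

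**What the plan says.** Section 7.2 orders Visit 3 as: questionnaires including CLUE (3.4), entrance acuity (3.7), binocular over-refraction (3.8), toric fit (3.9), general fit (3.10), logMAR visual performance (3.11), routine lens removal (3.13).

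- Step 3.9: "If toric fit is unacceptable, remove, store, and label the lenses, and proceed to final evaluation".
- Step 3.10: "If either lens is deemed unacceptable, the subject will be discontinued from the study". The lenses then come off, a slit-lamp examination is done and the Final Evaluation form is completed.
- Step 3.11: "Visual performance will be recorded OD, OS, and OU for the following", followed by the ETDRS and Guillon-Poling charts.
- Table 3 in Section 7.1 has a row "Distance, Intermediate, and Near ETDRS LogMAR Visual Acuity", marked at Visit 3 only.
- Section 8.2, for discontinued subjects: "Complete the current visit (scheduled or unscheduled". Its only deferral to Section 7.2 concerns discarding used lenses.

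On analysis, Section 14.1 states "All analyses will be conducted on per-protocol population (see Section 14.3", and Section 14.3 defines that set as "All subjects who have successfully completed all visits and did not substantially deviate from the protocol". Section 14.9 imputes nothing in the main analysis and adds multiple imputation only when dropout exceeds 15%.

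**The concern.** A subject can wear the lenses for the full 12-16 days, attend Visit 3 and still contribute nothing to either acuity hypothesis, because a fit check a few minutes earlier ended the lens-on part of the visit. Failing step 3.9 means rotation beyond 40 degrees or poor stability with blink, and in a toric lens either can plausibly degrade vision. The missing values would then depend on the device performance that the study is meant to measure. With one arm and a fixed threshold, no comparator loses subjects in the same way, so dropping poor performers moves the mean towards success.

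There is also a conduct problem. A site that follows the step text and a site that follows Section 8.2 would produce different data for the same kind of subject.

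**Working it through.** **1. Is there any substitute for step 3.11?** Hypotheses 1 and 2 (Section 2.3) name ETDRS logMAR charts at distance and Guillon/Poling charts at near.

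| Source of acuity | What it gives | Usable for Hypotheses 1-2? |
|---|---|---|
| Visits 1-2, study-lens acuity | Snellen at distance at entrance and exit, ETDRS 2000 card at near; no logMAR battery in Table 3 | No |
| Step 3.7, entrance | Snellen at distance, ETDRS 2000 card at near | No |
| Step 3.11 | The named charts, study lens on | Yes, but after both fit exits |
| Final Evaluation, F.1 | Acuity with refraction, study lens off | No |

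CLUE is recorded at 3.4 and is not lost by lens removal. A subject discontinued at 3.10 is nevertheless likely to fall outside the per-protocol set. For a 3.9 exit the text does not settle this.

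**2. Planning inputs.** Section 14.2 gives SD 0.12 logMAR, two-sided alpha 0.05 and 36 completers. Section 2.3 gives thresholds of 0.10 (distance) and 0.17 (near). A one-sample t-test with exact noncentral t, using effect = threshold − true value, reproduces all nine rows of the Section 14.2 tables. For example, distance at true 0.00 gives n = 18, power 0.915, and near at true 0.10 gives n = 33, power 0.901. The same model is therefore used below, as a simplification of the planned mixed model.

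**3. Bias if exits are excluded.** The documents give no Visit 3 fit-failure rate and no acuity by fit status, so k and D are assumptions: k = 1 or 2 exits of 36, with acuity D = 0.10 to 0.30 logMAR worse than the other subjects.

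Bias in the mean = k × D / 36.

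With the all-subject mean exactly at the threshold, the chance that the upper 95% limit falls below it is a noncentral t probability on 35 − k degrees of freedom, with noncentrality (in the direction of success) bias / (0.12 / √(36 − k)).

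| k | D | Bias | Noncentrality | Chance of false success |
|---|---|---|---|---|
| 0 | – | 0 | 0 | 2.5% |
| 1 | 0.10 | 0.0028 | 0.0028/0.0203 = 0.14 | 3.4% |
| 1 | 0.30 | 0.0083 | 0.0083/0.0203 = 0.41 | 5.9% |
| 2 | 0.10 | 0.0056 | 0.0056/0.0206 = 0.27 | 4.5% |
| 2 | 0.30 | 0.0167 | 0.0167/0.0206 = 0.81 | 12.0% |

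**4. If the same subjects are measured and included.** A simulation of 200,000 runs per setting, with exit probability 1/36 or 2/36 and the same D, gives about 2.5-3.2%. With exits excluded it agrees with the table.

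**5. Would the plan's safeguard catch it?** 1/36 = 2.8% and 2/36 = 5.6%. Neither reaches the 15% trigger by itself. An intent-to-treat set is defined in Section 14.3, but Section 14.1 assigns no analysis to it.

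**The case against.** The strongest counter-arguments are these.

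- **Few subjects may be affected.** Fit is checked at Visits 1 and 2, and Visit 2 dispensing (step 2.29) requires that "Lenses must have an acceptable toric and general lens fit" and that distance acuity be 20/30 or better. This stands: the number could be zero.
- **The figures take the least favourable case.** They put the true mean at the threshold, and 12% is the extreme corner. At the planning values with 36 completers, the same biases raise the chance of success only from 0.973 to at most 0.995 (distance 0.02) and from 0.925 to at most 0.983 (near 0.10). The effect is larger only at the pessimistic rows (distance 0.05, near 0.12): 0.681 to 0.715-0.882. The hyperopic studies in Section 1.5 had means no worse than 0.066 at distance and 0.103 at near, leaving 0.034 and 0.067 to the thresholds, both more than 0.017. This also stands as a statement of likely size.
- **The direction is less sure for step 3.10.** Its criteria are mechanical, and one failing lens may leave binocular acuity intact. This is fair, so the bias is plausible and not demonstrated.
- **Section 8.2 may already require step 3.11, and the fit wording may be carried over from visits where it gates further wear.** Even so, the step text takes the lenses off first, and a site cannot follow both. The carry-over reading strengthens the case for correcting the text.
- **Per-protocol-only analysis is a wider issue.** This is true, and the present fix does not recover fit failures at Visits 1 and 2. It does prevent an avoidable loss among subjects who completed the wear period.

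**Conclusion.** The concern holds. Read literally, steps 3.9 and 3.10 prevent the only logMAR measurement in subjects whose fit fails at Visit 3, nothing else in the study replaces it, and Section 8.2 contradicts the step text. The loss is tied to device performance, and neither the per-protocol analysis nor the 15% trigger would correct it.

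The size is unknown. Under the assumed 1-2 exits of 36 and a deficit of 0.10-0.30 logMAR, the mean is too good by 0.003-0.017 logMAR, and the false-success rate at the threshold is 3.4-12% against a nominal 2.5%. Well inside the threshold the effect on the conclusion is small. The cost in power is minor; selection is the problem. The change should be made because it is cheap and the missing data cannot be recovered after the visit. Confidence is medium, given the unknown frequency.

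**What to change.** 1. At Visit 3, place step 3.11 before steps 3.9 and 3.10. Leave the fit criteria and the lens-removal rules as written.
2. Reconcile steps 3.9 and 3.10 with the instruction in Section 8.2 on completing the current visit, so that every site does the same thing.
3. State in Sections 14.3 and 14.5 that a subject who reaches Visit 3 and has logMAR acuity measured is included in the primary acuity analysis whatever the Visit 3 fit result. If the sponsor keeps the present order, state instead how these subjects enter the acuity analysis, whatever the dropout rate.

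The cost is a reordering of steps and eCRF pages within one visit, plus a sentence each in Section 8.2 and Section 14. No procedure is added: subjects who would have left early complete an acuity test already planned for everyone at that visit.

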7.3. Unscheduled Visits

If, during the investigation, a subject requires an unscheduled visit to the clinical site, the following information will be collected at a minimum:

- Chief complaint prompting the visit. If the reason is an adverse event, the applicable eCRF for the adverse event must be completed and subject record completed as appropriate
- Date and time of the visit and all procedures completed at the unscheduled visit
- Review of adverse event and concomitant medications
- Documentation of any test article dispensed or collected from the subject, if applicable
- Slit lamp findings (using the Slit Lamp Classification Scale)

If the Investigator withdraws a subject from the study, the final study visit case report forms must be completed indicating the reason(s) why the subject was withdrawn. The subject record must be completed documenting the date and primary reason for withdrawal and the study CRA notified.

Any ocular and non-ocular Adverse Events that are ongoing at the time of the study visit will be followed by the Investigator, within licensure, until they have resolved, returned to pre-treatment status, stabilized, or been satisfactorily explained. If further treatment i.e., beyond licensure is required, the subject will be referred to the appropriate health care provider.

The following information will be collected during an unscheduled visit.

Unscheduled Visit			
Step	Procedure	Details	
U.1	Chief Complaints	Record the subject's chief complaints for reasons for the unscheduled visit.	
U.2	Adverse Events and Concomitant Medications Review	Review any changes to the subject's medical history or concomitant medications from the previous study visit. Record any changes, and any adverse events.	

Unscheduled Visit			
Step	Procedure	Details	
U.3	Subject Reported Ocular Symptoms	Subjects will respond to a verbal open-ended symptoms questionnaire.	
U.4	Entrance Visual Acuity	Record the entrance distance and near visual acuity (OD, OS and OU) to the nearest letter. For near measures use the ETDRS 2000 Series Chart 1 or 2. The acuity will be recorded to the nearest letter OD, OS and OU.	
U.5	Subjective Sphero-cylindrical Refraction	An optimal, binocular balanced distance sphero-cylindrical refraction will be performed. Record the refraction and distance visual acuity to the nearest letter.	
U.6	Slit Lamp Biomicroscopy	FDA Slit Lamp Classification Scale will be used to grade the findings and determine eligibility. For the conjunctival redness [REDACTED] 0.5-unit increments will be used in the grading. Corneal Staining Assessment [REDACTED] will be graded in 1.0 increments. If the clearance of the fluorescein needs to be expedited, preservative-free rewetting drops or saline may be instilled.	
U.7	Lens Dispensing	Additional study lenses may be dispensed when required.	
U.8	Toric Fit Evaluation	After lens settling, record: 
 • The rotational position to the nearest degree • Lens stability with blink • Lens stability with eye versions • Toric fit acceptable or unacceptable Toric lens fit will be unacceptable if lenses rotated more than 40 degrees, or lens stability is worse than 5 degrees movement with blink. If toric fit is unacceptable, remove, store, and label the lenses, and proceed to final evaluation. 	
U.9	Subjective Lens Fit Assessment	Evaluate and grade lens centration, primary gaze movement, upgaze movement and tightness (push-up test). 
 • The subject should not proceed to wear the 	

Unscheduled Visit			
Step	Procedure	Details	
		
lenses if any of the following is observed:
 
 • presence of limbal exposure (appearance of clear cornea) in any gaze • presence of edge lift • presence of unacceptable movement (excessive or insufficient) in all three movement categories (primary gaze, upgaze, and push-up). 
If either lens is deemed unacceptable, the subject will be discontinued from the study. Remove the lenses, perform a slit-lamp evaluation, and complete the Final Evaluation form.
	
U.10	Exit Visual Acuity	
Record the entrance distance and near visual acuity (OD, OS and OU) to the nearest letter.
 
For near measures use the ETDRS 2000 Series Chart 1 or 2. The acuity will be recorded to the nearest letter OD, OS and OU.
	

7.4. Laboratory Procedures

Not Applicable.

8. SUBJECTS COMPLETION/WITHDRAWAL

8.1. Completion Criteria

Subjects are considered to have completed the study if they:

- provided informed consent
- they are eligible
- completed all visits

8.2. Withdrawal/Discontinuation from the Study

A subject will be withdrawn from the study for any of the following reasons:

- Subject death during the study period
- Subject withdrawal of consent
- Subject not compliant to protocol
- Subject lost to follow-up
- Subject no longer meets eligibility criteria (e.g. the subject becomes pregnant)
- Subject develops significant or serious adverse events causing discontinuation of study lens wear
- Subjects who have experienced a Corneal Infiltrative Event (CIE)

- Investigator's clinical judgment regarding the subject safety reasons (that it is in the best interest of the subject to stop treatment)
- Subject missed two consecutive study visits
- Subject not compliant with study lens wear schedule
- Subject not successfully dispensed due to lack of efficacy and safety including poor vision, poor comfort or unacceptable fit

For discontinued subjects, the Investigator will:

- Complete the current visit (scheduled or unscheduled)
- Complete the Final Evaluation, indicating the reason that the subject was discontinued from the study
- Record the spherocylindrical refraction with best corrected distance visual acuity
- Collect used test article(s) (worn or brought to the visit) from the subject and discard them, unless otherwise stated in Section 7.2
- Collect all unused test article(s) from the subject

An additional subject may be enrolled if a subject discontinues from the study prematurely.

In cases where a subject is lost to follow-up, every possible effort must be made to contact the subject and determine the reason for discontinuation/withdrawal. The measures taken to follow up must be documented including two written attempts and a certified letter (or equivalent) as the final attempt.

